5.1.3 Study Week/Month Windows

For all the efficacy analysis with two assessment at month 3 and month 6 including [redacted] healthcare utilization record evaluation, [redacted] [redacted], [redacted], analysis windows for Month 3 LOCF and Month 6 LOCF are defined as the last assessment within in the timeframe defined in [Table 5.1.3-1](#). [redacted]

[redacted] Healthcare utilization record evaluation, [redacted] [redacted]

will be performed for timepoints at Month 3 LOCF, Moth 6 LOCF and Last visit.

Table 5.1.3-1 Mapping of Trial Windows A	
Visit	Number of Trial Days in Each Phase
	Window (days)
Month 3	68- 97
Month 3 LOCF	1 – 97
Month 6	135 - 182
Month 6 LOCF	98 - 182

Protocol 31-201-301 Interim Analysis Plan

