During the assessment period, subjects will visit the investigator for clinical evaluations at baseline (Day 1), Month 3, and Month 6/early termination (ET). Monthly assessments will follow a 28-day schedule, and at each visit and at any unscheduled visits, the subject's clinical status will be evaluated. All hospitalizations and all interventions (psychiatric only as well as pharmacy cost of all medications) will be recorded, in addition to all other assessments outlined in this protocol. The primary endpoint will be assessed at Month 3. The final trial visit will be on Month 6/ET and will be followed by a 30-day (\pm 3 day) safety follow-up period for subjects continuing on Abilify MyCite. For subjects completing Months 4 to 6 on standard of care, a 30-day safety follow-up period is not required. Subjects will also visit the clinic for medication dispensing and accountability at Months 1, 2, 4, and 5. Any treatment changes, including reason for the change, will be recorded in the electronic case report form (eCRF).

Evaluation of safety and tolerability of Abilify MyCite as assessed by frequency and severity of the AEs to be collected in this trial, ie, serious AEs (SAEs), device-related nonserious AEs, potential hepatotoxicity cases, and pregnancies.

Subject use of the Abilify MyCite system can be monitored by their respective investigators, who are suggested to review the physician dashboard data at a minimum of every 2 weeks and make changes to current treatment plan and therapy at their discretion. The investigators may request that a subject return to the site for unscheduled visits as deemed appropriate. In the event of an unscheduled visit, review of the investigator dashboard and safety events will be collected.

Protocol 031-201-00301

Safety Follow-up

All subjects who complete or withdraw from the trial while on Abilify MyCite (unless they have withdrawn their consent for participation in the trial) will receive a telephone call for safety follow-up at 30 days (\pm 3 days) after the last trial visit.

This telephone contact will be made to assess if there were any AEs experienced since the last trial visit. In addition, the subject will be asked about any new medications or changes in existing medications and the information will be documented. The trial design is presented in [Figure 3.1-1](#).

Protocol 031-201-00301

[figure not shown]

Figure 3.1-1 Trial Design Schematic

Note: Monthly assessments will follow a 28-day schedule.

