3.7.1.3.3 Month 3 Visit

Month 3 (- 3/ + 2 days) will be an investigator visit for the subject. At the Month 3 visit, the following will be performed:

- Administer the suicidality assessment (C-SSRS Since Last Visit Version; [Section 3.7.3.5](#)).
- Perform vital signs assessment ([Section 3.7.3.3](#)).
- Monitor AEs, including device-related nonserious AEs ([Section 5](#)).
- Abilify MyCite products (aripiprazole tablet embedded with an IEM sensor), supplies, and patches (prescribed dose is recorded) sufficient for 1 month will be dispensed. Any treatment changes, including reason for the change, will be recorded in the eCRF.
- Accountability of patches and Abilify MyCite product (aripiprazole tablet embedded with an IEM sensor) supplies performed.

Protocol 031-201-00301

- Review Abilify MyCite dashboard data every 2 weeks.
- [REDACTED]
- [REDACTED]
- [REDACTED]
- Healthcare utilization record evaluation ([Section 3.7.1.4](#)).
- [REDACTED]
- [REDACTED]
- [REDACTED]
- [REDACTED]

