5.1.2 Definition of Baseline and Last Visit

The following definitions of baseline values are applicable to all efficacy analysis and safety analysis unless otherwise specified.

Baseline values are defined as the last available evaluations prior to or on the date of the first MyCite treatment.

Last visit is defined as the last scheduled visit with available data.

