5.1.4 Handling of Missing Data

5.1.4.1 Criteria for Potential Values for Scale Assessments

In order to assess sensitivity of results due to missing data, 2 types of data sets will be used to perform analyses by visit of mean change from baseline endpoints: last observations carried forwarded (LOCF) and observed cases (OC). The LOCF data set will include data recorded after baseline, if no observation is recorded at that visit, data carried forward from the immediately previous visit (scheduled or unscheduled) will be used to impute for the missing observations. Baseline data will not be carried forward to impute missing values for the LOCF data set. The OC data sets will also be used to perform efficacy analyses and as the primary data sets for safety analyses. The OC data set corresponding to a visit will consist of data from all patients who were evaluated at that visit, i.e., patients with missing data due to dropout or other reasons will not be included in the OC data set.

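### Month 6 LOCF is limited to Days 98-182, so it cannot carry forward any Month 3 or earlier value, contrary to the SAP's own carry-forward rule (minor)

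*SAP*

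**What the plan says.** Two adjacent parts of the SAP define what an LOCF value is.

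- **Section 5.1.3 and Table 5.1.3-1.** For efficacy endpoints assessed at Months 3 and 6, "analysis windows for Month 3 LOCF and Month 6 LOCF are defined as the last assessment within in the timeframe defined in" the table. The windows are Month 3, Days 68-97; Month 3 LOCF, Days 1-97; Month 6, Days 135-182; Month 6 LOCF, Days 98-182. The results are reported at Month 3 LOCF, Month 6 LOCF and the last visit.
- **Section 5.1.4.1.** LOCF and observed-case (OC) data sets are both built to show how sensitive the change-from-baseline results are to missing data. For LOCF, where a visit has no observation, "data carried forward from the immediately previous visit (scheduled or unscheduled) will be used to impute for the missing observations". The section also says "The LOCF data set will include data recorded after baseline" and "Baseline data will not be carried forward to impute missing values for the LOCF data set".

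Section 5.1.2 places baseline on or before the first treatment day: "Baseline values are defined as the last available evaluations prior to or on the date of the first MyCite treatment". Protocol 3.1 schedules clinical evaluations at Day 1, Month 3 and Month 6 or early termination (ET), and states that "Monthly assessments will follow a 28-day schedule". Protocol 3.7.1.3.3 sets the visit window: "Month 3 (- 3/ + 2 days) will be an investigator visit for the subject".

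**The concern.** The scheduled clinical evaluation before Month 6 is Month 3. If Month 6 is missing, the Month 3 value is the one that the rule in 5.1.4.1 would normally carry forward. A window that opens on Day 98 shuts it out. Two programmers, one working from the table and one from the rule, would build different Month 6 LOCF data sets.

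What is at stake is the purpose of the LOCF data set. OC leaves out subjects with no Month 6 assessment, and LOCF is there to bring them back. If Month 6 LOCF also leaves out everyone last assessed by Day 97, agreement between the two analyses gives little reassurance about those subjects. SAP 7.4.1.1 tests change from baseline with paired t-tests, so the choice of data set reaches reported p-values as well as descriptive tables.

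**Working it through.** No power or alpha figure is involved. The check places visit days in the windows and compares the value chosen by the table with the value chosen by the rule.

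**1. Visit days.** Inputs are the 28-day month (Protocol 3.1) and the -3/+2 day window (Protocol 3.7.1.3.3 and 3.7.1.3.5). The documents can be read as placing month m on Day 28m or on Day 28m + 1, so both are shown.

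- Month 3: 28 × 3 = 84, giving Days 81-86; or Day 85, giving Days 82-87.
- Month 6: 28 × 6 = 168, giving Days 165-170; or Day 169, giving Days 166-171.

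Under either count the Month 3 visit lies wholly inside Days 1-97 and wholly outside Days 98-182. The Month 6 visit lies inside both Month 6 windows.

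**2. What Month 6 LOCF adds to OC.** The Month 6 LOCF window has 182 - 98 + 1 = 85 days. The Month 6 window has 182 - 135 + 1 = 48 days. The difference is 85 - 48 = 37 days, namely Days 98-134. The Month 3 LOCF and Month 6 LOCF windows share no day.

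**3. Table against rule.** The entry is the day of the value used; none means no value.

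| Assessments held | Month 6 LOCF by table | Month 6 LOCF by 5.1.4.1 | Month 3 LOCF, table plus baseline bar |
|---|---|---|---|
| Day 1, Day 85, Month 6 missing | none | 85 | 85 |
| Day 1, ET on Day 40 | none | 40 | 40 |
| Day 1, Day 85, ET on Day 120 | 120 | 120 | 85 |
| Day 1, Day 85, Day 169 | 169 | 169 | 85 |
| Day 1 only | none | none | none |

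Table and rule disagree at Month 6 in the first two rows, where nothing was assessed after Day 97. They agree in the others.

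**4. Lower bound at Month 3.** Day 1 is normally the baseline day and is also the first day of the Month 3 LOCF window. On the table alone, the Day-1-only subject would receive the Day 1 value. Section 5.1.4.1 excludes that value, so the subject has no Month 3 LOCF value.

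The two boundaries differ in kind. At Month 3 the table admits a value that the text then prohibits, so both can be applied together. At Month 6 the table excludes a value that the text requires, so both cannot be applied.

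**The case against.** The best defence is that the Day 98 floor is deliberate. Healthcare utilization is the one endpoint legible in 5.1.3, and for a record that covers a period, a floor that keeps Months 1-3 out of Months 4-6 makes sense. Section 5.1.4.1 is headed as concerning scale assessments, and Month 3 is also when the investigator decides on further treatment. Other endpoints named in 5.1.3 are blacked out, so which rule governs which endpoint cannot be fully seen. This is plausible, but the visible text of 5.1.3 applies the windows to all efficacy analyses with assessments at the two months and makes no such split. If that is the intention, it needs stating.

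Three qualifications stand. Assessments on Days 98-134, including ET visits, do count at Month 6. The last-visit time point has no Day 98 floor and can use Month 3 data, though 5.1.2 confines it to scheduled visits while 5.1.4.1 also admits unscheduled ones. Kaplan-Meier time to discontinuation is planned as well, so dropout is not hidden from the report.

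A reader might infer two stronger things.

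- **That Month 3 LOCF gives subjects with only baseline data a change of zero, diluting the mean change.** The documents do not support this: 5.1.4.1 limits LOCF to post-baseline data and bars carrying baseline forward.
- **That the gap between 320 enrolled and 224 completing (Protocol 3.3) is the number lost from Month 6 LOCF.** This does not follow. SAP 7.4.1.1 uses an Efficacy Sample that the SAP does not define. Protocol 7.2 restricts it to subjects who completed three months of dosing, so non-completers would already be outside it. Protocol 3.8.3.1 also seeks follow-up of early discontinuers for the whole trial, so stopping treatment is not the same as having no assessment after Day 97. Conversely, some three-month completers may have none.

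**Conclusion.** The Month 6 contradiction is real. For a subject with a post-baseline assessment by Day 97 and none on Days 98-182, Table 5.1.3-1 gives no Month 6 LOCF value and 5.1.4.1 gives one. The tabulated window extends OC by 37 days and is otherwise the same window, so it is a weak check on missing data for subjects last seen by Day 97. The number affected cannot be derived from the documents.

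At Month 3 the only issue is a lower bound that should be tidied to match the text.

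The point is minor. The primary McNemar comparison (SAP 7.1.1) does not use LOCF, and PDC (SAP 7.2) is calculated over 84 or 168 days, so neither depends on these windows. The conclusion rests on the visible text of 5.1.3 and on Month 3 visits being held within their protocol window. A visit delayed to Day 98 or later would fall in the Month 6 LOCF window.

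**What to change.** For change-from-baseline endpoints, amend Table 5.1.3-1 as follows:

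- Month 6 LOCF: the last post-baseline assessment through Day 182.
- Month 3 LOCF: the last post-baseline assessment through Day 97, with the window starting after baseline.

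If the Day 98 floor is intended for period-based data such as healthcare utilization, keep it in a separate row for those data only and say so in one sentence of 5.1.3.

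The cost is two lower bounds in one table, plus a row and a sentence if the floor is kept for utilization. No extra data are needed, and the primary and PDC analyses do not change.

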5.1.4 Handling of Missing Data

5.1.4.1 Criteria for Potential Values for Scale Assessments

In order to assess sensitivity of results due to missing data, 2 types of data sets will be used to perform analyses by visit of mean change from baseline endpoints: last observations carried forwarded (LOCF) and observed cases (OC). The LOCF data set will include data recorded after baseline, if no observation is recorded at that visit, data carried forward from the immediately previous visit (scheduled or unscheduled) will be used to impute for the missing observations. Baseline data will not be carried forward to impute missing values for the LOCF data set. The OC data sets will also be used to perform efficacy analyses and as the primary data sets for safety analyses. The OC data set corresponding to a visit will consist of data from all patients who were evaluated at that visit, i.e., patients with missing data due to dropout or other reasons will not be included in the OC data set.

5.1.4.2 Partial Dates for Hospitalization

In the event that only partial dates (missing day or month, but not year) are available for the hospitalization and medical intervention record during the retrospective or prospective periods (including the admission and discharge date of inpatient hospitalizations, start and end date of psychiatric non-inpatient treatment visits, and the emergency room and/or outpatient treatment visit date), the following rules will be used to impute missing month or day:

a) For partial admission/start/visit dates:

1. If only the month is missing:

If the admission/start/visit year equals to the corresponding (retrospective or prospective) period Month 1-3 start year, then the earliest corresponding period for Month 1-3 start month that will cover this event in this period will

Protocol 31-201-301 Interim Analysis Plan

be imputed for the missing month. If the admission/start/visit year equals to the corresponding (retrospective or prospective) period Month 4-6 start year, then the earliest corresponding period for Month 4-6 start month that will cover this event in this period will be imputed for the missing month. Otherwise, default to 'Jan'.

2. If only the day is missing:

If the admission/start/visit year equals to the corresponding (retrospective or prospective) period Month 1-3 start year and admission/start/visit month equals to the corresponding period Month 1-3 start month, the corresponding period Month 1-3 start day or '01' will be imputed for the missing day so that the final date will be within the Month 1-3 period. If the admission/start/visit year equals to the corresponding (retrospective or prospective) period Month 4-6 start year and admission/start/visit month equals to the corresponding period Month 4-6 start month, the corresponding period Month 4-6 start day or '01' will be imputed for the missing day so that the final date will be within the Month 4-6 period. Otherwise, default to '01'.

3. If both month and day are missing:

If the admission/start/visit year equals to the corresponding (retrospective or prospective) period Month 1-3 start year, the day will be imputed as 15th and then the month will be imputed following Scenario 1. If the admission/start/visit year equals to the corresponding (retrospective or prospective) period Month 4-6 start year, the day will be imputed as 15th and then the month will be imputed following Scenario 1. Otherwise default to Jan. 01.

b) For partial discharge/end dates:

1. If only the month is missing:

Default to the same month or the following month of the admission/start date, whichever imputes an earlier date that is after the admission/start date. However, if a patient died and the discharge/end year equals to the year the subject died, default to the month the patient died, or the same month or the following month of the admission/start date, whichever imputes an earlier date that is after the admission/start date.

2. If only the day is missing:

If a patient died, and if the discharge/end year equals to the year the patient died and discharge/end month equals to the month the patient died, the day the subject died will be imputed for the missing day. Otherwise, default to the last day of the discharge/end month.

3. If both month and day are missing:

The day will be imputed as 15th and then the month will be imputed following Scenario 1.

Protocol 31-201-301 Interim Analysis Plan

6 Disposition and Demographic Analysis

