7.1.2 Technical Details

Inpatient psychiatric hospitalization is defined as closed (locked) ward or open ward inpatient psychiatric hospitalization, where the hospitalization is not primarily for psychosocial reasons.

The start date and end date of the retrospective period Months 1-3 are calculated in the following ways: start date = (Date signing informed consent - 28*6 Days) and end date = (Date of signing informed consent - 28*3-1 Days). The start date and end date of the prospective period Months are calculated as: start date = (Mycite start date) and end date = (Mycite start date + 28*3 - 1). Similarly, the start date and end date of the retrospective period Months 4-6 are calculated in the following ways: start date = (Date signing informed consent - 28*3 Days) and end date = (Date of signing informed consent -1 Days). The start date and end date of the prospective period Months are calculated as: start date = (Mycite start date + 28*3) and end date = (Mycite start date + 28*6 - 1).

Inpatient psychiatric hospitalization is deemed to occur during the retrospective (or prospective) Months 1-3 if:

- The hospitalization starts before the start date of retrospective (or prospective) Months 1-3 and continues into Months 1-3
- The hospitalization starts during the retrospective (or prospective) period.

Similarly, Inpatient psychiatric hospitalization is deemed to occur during the retrospective (or prospective) Months 4-6 if:

- The hospitalization starts before the start date of retrospective (or prospective) Months 4-6 and continues into Months 4-6
- The hospitalization starts during the retrospective (or prospective) period

All the above hospitalization in Months 1-3 and Months 4-6 will be counted in the Month 1-6 period.

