7.4.1.2 Technical Details

Number of inpatient psychiatric hospital stays per subject during the 3 months (Months 1-3) of the retrospective (or prospective) period is determined as the total number of inpatient psychiatric hospitalization, closed (locked) ward or open ward, but not primarily for psychosocial reasons for each subject during the respective/retrospective periods. Cumulative duration of inpatient psychiatric hospitalization per subject is the sum of duration of each reported inpatient psychiatric hospitalization for each subject, which is defined as $\min(\text{Date of Discharge, End date of the 3-months of the respective period}) - \max(\text{Start Date of Admission, Start date of the 3-months of the respective period}) + 1$. Mean duration of inpatient psychiatric hospitalization per subject is derived as the cumulative duration divided by the number of inpatient psychiatric hospitalization for each subject. If a subject did not experience any inpatient psychiatric hospitalization during the 13-months, zero will be assigned to his/her number of inpatient psychiatric hospital stays, and to his/her cumulative and mean duration of inpatient psychiatric hospitalization. Similarly, method will be used to analyze the cumulative duration of inpatient psychiatric hospitalization and mean duration of inpatient psychiatric hospitalization during Month 1-6.

Inpatient hospitalizations for psychosocial reasons are defined as inpatient psychiatric hospitalization, closed (locked) ward or open ward, where hospitalization is primarily psychosocial reasons. For the last 3 months (Months 4-6) of the retrospective (or prospective) period, number and cumulative or mean duration of inpatient hospitalizations for psychosocial reasons are derived in similar ways to those of inpatient psychiatric hospitalization.

Number and cumulative or mean duration of inpatient non-psychiatric hospitalizations during the 3 months (Months 1-3) of the retrospective (or prospective) period are derived in similar ways to those of inpatient psychiatric hospitalization.

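### SAP 5.1.4.2 fills in a missing admission day without looking at a known discharge date, so stays can land in the wrong three-month window and get zero or negative lengths

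*SAP*

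**What the plan says.** SAP 5.1.4.2 covers partial dates in the hospitalisation record, "including the admission and discharge date of inpatient hospitalizations". Three of its rules matter here.

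- **Rule a.2 (admission day missing).** If year and month match the month in which Months 1-3 opens, the day "will be imputed for the missing day so that the final date will be within the Month 1-3 period". If they match the month in which Months 4-6 opens, the day "will be imputed for the missing day so that the final date will be within the Month 4-6 period". In practice this is the window's opening day, because the first of the month precedes the window unless the window opens on the first. The discharge date plays no part.
- **Rule b.2 (discharge day missing).** After an exception for a death in that month: "Otherwise, default to the last day of the discharge/end month".
- **Rule b.1 (discharge month missing), and b.3, which refers back to it.** The imputed discharge is chosen by "whichever imputes an earlier date that is after the admission/start date". This is the only date-order condition in the section.

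SAP 7.1.2 opens retrospective Months 1-3 at 168 days before consent ("start date = (Date signing informed consent - 28*6 Days") and closes it 85 days before consent. Months 4-6 follow. A stay is an event in a window if it is admitted there, with no condition on discharge, or if "The hospitalization starts before the start date of retrospective (or prospective) Months 1-3 and continues into Months 1-3". SAP 7.4.1.2 computes length of stay as the earlier of discharge and window end, minus the later of admission and window start, plus 1, with no floor at zero.

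**The concern.** The primary endpoint is a yes/no for each subject in each Months 1-3 window, so a rule that decides which window a stay belongs to also decides the endpoint. Rule a.2 can override a recorded discharge date with an admission date that cannot be true. Rule b.2 always resolves an unknown in favour of counting the stay. Nothing downstream catches either: the event definition does not test discharge against window start when the admission is in the window, and the duration formula accepts a discharge before the admission.

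At stake are misclassified pairs in the McNemar table and, separately, impossible values in the exploratory number-of-days endpoints, where they would lower cumulative and mean stay.

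**Working it through.** **1. The plan's yardstick.** The SAP gives no figure for the date rules, so the planned effect is the scale. With 13.5% and 5% in the discordant cells, the difference is 8.5 points and total discordance is 18.5%. N = (1.960·√0.185 + 0.842·√(0.185 − 0.085²))² / 0.085² = 198.6, which agrees with the stated 200 for 80% power.

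**2. Worked dates.** Take consent on 4 September 2019. Retrospective Months 1-3 runs from 20 March to 11 June, and Months 4-6 opens on 12 June.

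| Recorded stay | Imputed under SAP | Result under SAP | What the known dates show |
|---|---|---|---|
| Admitted ?? June, discharged 10 June | Admission 12 June | Not in Months 1-3; Months 4-6 length 10 − 12 + 1 = −1 day | Wholly in June before the 12th, so in Months 1-3 |
| Admitted ?? March, discharged 12 March | Admission 20 March | Event in Months 1-3; length 12 − 20 + 1 = −7 days | Ended before Months 1-3 |
| Admitted 4 March, discharged ?? March | Discharge 31 March | Event in Months 1-3; length 31 − 20 + 1 = 12 days | Cannot be determined: a discharge on 4-19 March is outside, on 20-31 March inside |
| Admitted ?? March, discharged ?? March | 20 to 31 March | Event in Months 1-3; 12 days | Cannot be determined |

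Under a.2, a discharge on the day before the window opens gives length 0; any earlier discharge gives a negative length. Rule b.2 produces no negative lengths.

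**3. Counting both directions.** Let the window open on day D of its month and let stays last L days, with one stay starting on each calendar day. Then 84 + L − 1 stays truly touch Months 1-3. If every day of the relevant kind were missing:

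- a.2 wrongly brings in the opening-month stays that ended before D: max(0, D − L).
- a.2 wrongly sends out every stay admitted before D in the month in which Months 4-6 opens: D − 1.
- b.2 wrongly brings in every stay discharged before D in the opening month: D − 1.

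Averaged over 365 consent dates (L is an assumption):

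| L | True stays | a.2 in | a.2 out | b.2 in |
|---|---|---|---|---|
| 5 | 88 | 11.05 | 14.78 | 14.72 |
| 10 | 93 | 7.20 | 14.78 | 14.72 |
| 15 | 98 | 4.17 | 14.78 | 14.72 |

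Of the false a.2 entries, about 92%, 91% and 88% have negative length; the rest are zero. The outflow includes stays whose known discharge proves the error (about 7 of 14.78 at L = 10, by the same max(0, D − L) count) and stays running into Months 4-6 whose status is truly unknown.

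**4. Scale on the retrospective rate.** Assume 10% of days missing, one stay per subject and the planned 15.5% rate. For L = 10:

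- a.2 in: 15.5 × 0.10 × 7.20/93 = +0.12 points
- a.2 out: 15.5 × 0.10 × 14.78/93 = −0.25 points
- b.2 in: 15.5 × 0.10 × 14.72/93 = +0.25 points

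For L = 5 the same products are +0.19, −0.26 and +0.26; for L = 15, +0.07, −0.23 and +0.23. Rule a.2 alone therefore nets −0.07, −0.13 and −0.17 points for L = 5, 10 and 15. All figures scale with the missing-day rate.

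**5. A bound on the test, for illustration.** Suppose b.2 acted with no offset and every extra event were retrospective-only: +0.25 points, N = 224, a single two-sided 5% test, no true effect. The rejection rate in the favourable direction, Φ((d√N − 1.96√p) / √(p − d²)), where d is the added difference and p the resulting discordance, goes from 2.5% to 3.0% (base discordance 18.5%) or 3.3% (10%).

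**The case against.** **Scope.** SAP 5.1.4.2 speaks of records in the retrospective or prospective periods, so a stay known to have ended before the window opened may not be such a record. Collection is also uncertain. Protocol 3.1 asks for psychiatric history for the 6 months before screening, which is 13 to 16 days longer than the 168-day window. Protocol 3.7.1.4 counts 6 months back from baseline, which may not reach the window opening after a long screening period. This makes the inflow conditional on such stays being in the dataset. It does not touch the Months 4-6 clause: a stay known to have ended in Months 1-3 lies inside the retrospective period on any reading.

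**Analysis set.** The primary analysis uses the mITT sample, which requires full hospitalisation information (SAP 5.1.1). If a partial date fails that condition, the primary test is largely protected. The SAP does not say so, and a section that imputes such dates suggests they are kept.

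**Direction.** A reader might infer that the errors inflate the pre-switch rate and favour the product, perhaps because old stays are recalled less exactly. The documents do not support this. They do not describe the retrospective stays as recalled, they do not say where missing days occur, and a.2 on its own removes more Months 1-3 events than it adds.

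**Size.** Within the affected subsets the shares look large. A simulation with window start and admission day uniform in a 30-day month and mean stays of 5 to 14 days puts 21% to 35% of day-missing opening-month admissions, and 63% to 77% of stays caught by b.2, before the window. A reader might take these as effects on the endpoint. They are shares of stays with a partial date in one calendar month, and step 4 shows how little remains on the rate.

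**Month end as a convention.** Replacing it with a midpoint would swap one convention for another where the truth is unknown. That objection stands, and the fix does not propose it.

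**Conclusion.** The concern holds as an internal fault in the date rules. Rule a.2 can put an admission after a recorded discharge, move a stay known to belong to Months 1-3 out of the primary endpoint, and count a stay known to precede Months 1-3 if it is in the data. Rule b.2 classifies stays whose window cannot be determined, always by counting them.

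The rules misassign only when the partial month is a window's opening month. Effects run in both directions, each about a quarter of a percentage point or less on the retrospective rate at an assumed 10% of days missing, against a planned 8.5. The net effect on the McNemar test is unknown and probably small, because the documents do not give the number of partial dates. Zero and negative lengths follow with certainty whenever a.2 meets a known earlier discharge, but they affect the exploratory stay-length endpoints and not the binary primary endpoint. The case for acting is that the plan should not overrule a recorded date, and that correcting it is nearly free.

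**What to change.** - **Rule a.2.** State that an imputed admission date may not be later than a known discharge date, and decide window membership from the known date first. Discharge before the Months 1-3 start: not in that window. Discharge before the Months 4-6 start: the stay remains in Months 1-3.
- **Undeterminable stays.** Where the known dates do not settle the window, including the b.2 cases and stays with both days missing, repeat the primary McNemar test with these stays counted in and counted out. Report how many there are.
- **mITT.** State in SAP 5.1.1 whether a partial date fails the full-information condition.
- **Protocol 7.3.** Reconcile SAP 5.1.4.2 with the protocol's statement that missing data for the primary variable are not imputed. That sentence also describes the primary variable as patch coverage, which is not the hospitalisation endpoint.

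Cost: SAP wording, a few lines of code and one sensitivity table. No new data are needed.
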